4.4 Withdrawal Criteria

All subjects have the right to withdraw from the study at any point during treatment without prejudice. The investigator can discontinue any subject at any time if medically necessary. It will be documented whether or not each subject completed the clinical study. If study treatment or observations were discontinued, the reason will be recorded and the Sponsor should be notified promptly. The reasons that a subject may discontinue participation in a clinical study could be from one or more of the following:

- AE(s)
- Death
- Subject withdrew consent
- Physician decision
- Lost to follow-up
- Initiation of protocol-prohibited lipid-lowering therapy (eg, an approved PCSK9 inhibitor)

The applicable reason(s) above will be recorded in the eCRF and subjects should be encouraged to complete the EOS visit. All data collected up until the time of subject withdrawal is to be entered into the electronic case report form (eCRF). Any withdrawn subjects will not be replaced in this study. No further follow-up is allowed with the subject to collect additional information following discontinuation from the trial.

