5.3 Medical Management Guidelines

5.3.1 Adverse events

Adverse events or abnormal test findings must be followed until the event (or its sequelae) or the abnormal test finding resolves, stabilizes at a level acceptable to the Sponsor/Investigator and/or returns to baseline values.

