## **2.7 Safety analyses**

The safety objectives of this study are to evaluate the safety and tolerability profile of long-term use of inclisiran.

Unless otherwise specified, safety evaluations will be performed for the Safety Population overall and by treatment group of the feeder studies.

Safety analyses are based on observed values and missing data will not be imputed.

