### **2.7.1.1 AEs of special interest (AESI) and additional safety topics**

#### **2.7.1.1.1 AEs at the injection site**

TEAEs at the injection site, which is an AESI, include all TEAEs identified as being an AE at the injection site on the AE page of eCRF or with “injection site reactions” as the high-level term (HLT).

The number of injection site TEAEs per subject will be summarized using descriptive statistics as well as the number of subjects with 0, 1, 2, 3, ... injection site TEAEs.

The following summaries will be presented for ORION-8 injection site TEAEs using number and percentage of subjects with the event:

- Overall Summary of TEAEs
- TEAEs by PT
- TEAEs by PT and maximum severity

- TESAEs by PT
- Signs and symptoms of TEAEs (only applicable to the events identified as AEs at the injection site on eCRF)
- TEAEs by PT and worst outcome

Outcomes of TEAEs ordered from worst to best will be:

- 1) Fatal
- 2) Not resolved
- 3) Resolved with sequelae
- 4) Unknown
- 5) Resolving
- 6) Resolved

For subjects whose injection site TEAEs are all resolved (i.e. the worst outcome for the subject is “Resolved”), the duration (in days) of injection site TEAEs will be summarized using descriptive statistics. If a subject has multiple durations, the median time will be used for that subject.

A subject data listing will be provided for injection site AEs. Such listing will include all AEs in ORION-8 database, regardless of whether they are ORION-8 TEAE.

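### Injection-site event duration is summarised only in subjects whose events all resolved, so its mean and upper tail are expected to be too short if some reactions persist

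*SAP*

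**What the plan says.** SAP 2.7.1.1.1 classes injection-site TEAEs as an adverse event of special interest. Its duration analysis opens with the restriction "For subjects whose injection site TEAEs are all resolved", which it explains as a worst outcome of 'Resolved' for the subject. For that subset, "the duration (in days) of injection site TEAEs will be summarized using descriptive statistics". It adds: "If a subject has multiple durations, the median time will be used for that subject". Under SAP 2.1 the descriptive statistics are n, mean, SD, median, quartiles, minimum and maximum.

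The same section plans a table of "TEAEs by PT and worst outcome", in which five outcome categories rank worse than 'Resolved': fatal, not resolved, sequelae, unknown and resolving. It also states: "A subject data listing will be provided for injection site AEs". SAP 2.7 sets the general rule: "Safety analyses are based on observed values and missing data will not be imputed".

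Two protocol rules determine which events can still be open at the end. Section 5.3.1 says "Adverse events or abnormal test findings must be followed until the event (or its sequelae) or the abnormal test finding resolves, stabilizes" (return to baseline is also accepted), so follow-up can end without resolution. Section 4.4 says "No further follow-up is allowed with the subject to collect additional information following discontinuation from the trial".

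Neither document gives a reason for the restriction, and neither plans a censored or sensitivity analysis of duration.

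**The concern.** Whether a subject enters the summary depends on the quantity being summarised. One event with any outcome other than 'Resolved' removes the whole subject, including that subject's resolved events. An event still open when observation stops is right-censored, and a long event is more likely to be in that state than a short one. Dropping such subjects, rather than censoring their events, is expected to shorten the reported durations.

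The subject-level median can conceal persistence separately. A subject with events of 3, 4 and 200 days contributes 4 days.

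Safety and tolerability of long-term use is a primary objective, and Protocol 1.3 names injection-site reaction as the only event known to be attributable to inclisiran. A long-term extension is the natural place to see whether a minority of reactions persist. A summary confined to resolved cases is poorly suited to showing that.

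**Working it through.** The plan states no figure for this summary, so there is nothing to reproduce. Two illustrations follow.

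**1. Worst-case bound.** Let q be the share of affected subjects excluded, and suppose that they are exactly those with the longest durations. The reported p-quantile is then the true p × (1 − q) quantile. The values of q are assumptions.

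| q | Reported median is true quantile | Reported Q3 is true quantile |
|---|---|---|
| 1% | 0.50 × 0.99 = 0.495 | 0.75 × 0.99 = 0.7425 (74th percentile) |
| 5% | 0.50 × 0.95 = 0.475 | 0.75 × 0.95 = 0.7125 (71st) |
| 20% | 0.50 × 0.80 = 0.40 | 0.75 × 0.80 = 0.60 (60th) |

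In days, for an assumed lognormal with median 5 and log-SD 1, the true Q3 is 5 × exp(0.674) = 9.8. At q = 5% the reported Q3 is 5 × exp(0.561) = 8.8, one day shorter.

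**2. Simulation of the rule.**

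- *From the documents:* dosing on Days 1, 90, 270, 450, 630, 810 and 990, and EOS at Day 1080 (Protocol Table 6-1).
- *Assumed:* 200,000 subjects with at least one event; 1, 2 or 3 events in 70%, 20% and 10% of them; durations lognormal with median 5 days and log-SD 1; a varying share of long events with median 365 days; 20% early discontinuation, unrelated to the reaction.

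Each cell gives the planned summary, then the value in all subjects with an event, in days. Both use subject-level medians, so the contrast isolates the exclusion.

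| Long events | Subjects excluded | Mean | Median | 90th percentile | 99th percentile |
|---|---|---|---|---|---|
| 0% | 0.4% | 8.0 / 8.1 | 5.2 / 5.3 | 16.8 / 16.9 | 45.6 / 46.3 |
| 2% | 1.6% | 11.0 / 19.0 | 5.3 / 5.4 | 18.0 / 19.1 | 108.3 / 321.2 |
| 5% | 3.3% | 15.6 / 34.8 | 5.5 / 5.6 | 20.4 / 24.6 | 280.5 / 739.4 |
| 10% | 6.3% | 23.0 / 62.6 | 5.7 / 6.1 | 27.1 / 80.8 | 416.7 / 1168.5 |
| 20% | 11.9% | 41.0 / 118.2 | 6.4 / 7.5 | 114.5 / 336.4 | 571.4 / 1701.9 |

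- With no long events and 40% discontinuation, 0.7% are excluded and the means are 8.0 and 8.1.
- With 5% long events and a further 2% of events counted as unresolved for reasons unrelated to length, exclusion rises to 6.1% but the planned mean stays at 15.6. The size of q alone does not determine the bias.
- The event-level Kaplan-Meier medians for the five rows are 5.0, 5.1, 5.3, 5.7 and 6.9.
- The all-subject values include time after observation ends, which no analysis can see. Kaplan-Meier recovers quantiles reached within follow-up, but not the full mean.

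**Scale.** If the roughly 5% frequency reported for ORION-1 (Protocol 1.2.2.2.2) carried over to the 2991 subjects enrolled (Protocol Amendment 2 rationale), about 0.05 × 2991 = 150 subjects would have an event. At q = 5%, 7 or 8 of them would be excluded.

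**The case against.** The restriction is openly stated, so the statistic is conditional by design. Unresolved cases appear in the worst-outcome table and the listing, and the summary's n against the number of subjects with events shows how many were left out. All of this is true and limits the scope to mislead, but none of it corrects the mean, Q3 or maximum in the duration table.

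What the protocol reports from earlier studies points to a small effect. ORION-1 reactions were short-lived, and EOS is planned at least 90 days after the last dose whenever possible. These are other studies and do not settle the matter here, but they make negligible bias a realistic outcome.

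A reader might go further and infer that the rule removes precisely the longest durations, can err only in the favourable direction, or always gives too low a maximum. The documents do not support these readings.

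- Unknown-outcome events, events that began shortly before an early EOS, and the resolved events of excluded subjects may all be short. Dropping them can lengthen the summary.
- A Day 1 reaction that resolved after 400 days stays in, while a reaction to the Day 990 dose still open at Day 1080, about 90 days, drops out.
- The subject median can exceed the subject's mean: for 1, 30 and 30 days it is 30, against 61/3 = 20.3.
- The reported maximum cannot be too high. It is too low only when the longest event is excluded or masked by the median.

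Nor does either document say that this figure will support a claim of short-lived reactions.

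**Conclusion.** The point holds as a minor one. Selection on resolution, with no censored analysis, is expected to understate the mean, upper quantiles and maximum if some reactions persist. In the assumed scenarios the planned mean is 8.0 against 8.1 days with no persistent events, and 15.6 against 34.8 when 5% of events are long. The median moves by at most 0.4 days until long events reach 20%, when it is 6.4 against 7.5. The direction rests on longer events being likelier to remain open; the size rests entirely on assumed duration distributions. The quantile shifts for q = 1%, 5% and 20% are an assumed worst case, not an estimate. The summary is descriptive and no efficacy result depends on it.

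**What to change.** Keep the planned table and add to SAP 2.7.1.1.1 an event-level Kaplan-Meier time to resolution covering all injection-site TEAEs:

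- Censor not resolved, resolving and unknown-outcome events at the last contact date, which SAP 2.1.1 already defines.
- State in advance whether resolution with sequelae counts as resolution.
- Allow for clustering of events within subject in any confidence interval.
- Report the median, Q3, the proportion unresolved at 30 and 90 days, each subject's longest observed duration, and the number of subjects excluded from the planned summary.

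The cost is SAP wording and one extra table, with no new data collection. Two cautions belong in a footnote. Censoring at discontinuation may be informative, since Protocol 4.4.1 lists severe or serious injection-site reactions among the reasons to interrupt or stop dosing. Censoring an unknown-outcome event at last contact treats it as still open until then, which may err towards longer durations.

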#### 2.7.1.1.2 Other AESIs and AEs of additional safety topics

Other AESIs include:

- Hepatic events
- Diabetes mellitus (see [Section 2.7.4](#) for additional analyses for diabetes)

Additional safety topics include:

- Renal events
- Hypersensitivity
- Neurological events and neurocognitive disorders
- Ophthalmological events
- Cardiac safety: Major adverse cardiovascular events (MACE) and each of the MACE components

See [Appendix 5.2](#) for the search criteria of each safety topic.

The following summaries of ORION-8 TEAEs will be presented for other AESIs and AEs of additional safety topics using number and percentage of subjects with the event:

- Overall Summary of TEAEs
- TEAEs by PT

- TEAEs by PT and maximum severity
- TEAEs possibly related to study drug by PT
- TESAEs by PT
- TEAEs leading to study drug withdrawal

Subject data listings will be provided for hepatic and diabetic AEs. Such listings will include all AEs in ORION-8 database, regardless of whether they are ORION-8 TEAE.

## 2.7.2 Deaths

As mentioned in [Section 2.7.1](#), TEAEs with a fatal outcome will be summarized by SOC and PT, and a subject data listing for AEs in ORION-8 database with a fatal outcome will be generated.

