3.1 Type/Design of Study

[figure not shown]
This study will be a long-term extension of the Phase II lipid lowering trial [MDCO-PCS-16-01 (ORION-3)] and Phase III lipid-lowering studies [MDCO-PCS-17-03 (ORION-9), MDCO-PCS-17-04 (ORION-10), or MDCO-PCS-17-08 (ORION-11)]. Up to 3300 subjects with atherosclerotic cardiovascular disease (ASCVD), ASCVD-risk equivalents (eg, diabetes and familial hypercholesterolemia), heterozygous [REDACTED] familial hypercholesterolemia (HeFH [REDACTED]) and elevated LDL-C despite treatment with LDL-C lowering therapies who are eligible and willing to participate may be enrolled. The objectives of the study is to evaluate the efficacy, safety, and tolerability of long-term dosing of inclisiran. Informed consent will be obtained from subjects before the initiation of any study-specific procedures. The EOS visit in the previous feeder studies will be Day 1 in the extension trial except for subjects enrolled in Sweden. Sweden Specific Protocol Amendment 1 (to Global Amendment 1 version, dated 1 Nov 2018) was implemented to allow limited lab tests to be done on Day 1 and to collect any safety information during the gap between feeder's EOS and Day 1 of this study until ethics committee approval was granted in that country. Subjects moving over from the open label ORION-3 study will not receive study medication at Day 1. Their first dose of study medication in this trial will be at day 90. This is to maintain their 6 months dosing schedule on inclisiran treatment. This trial will be a global, multicenter study in approximately 300 centers.

The duration that each subject is expected to participate in this study is a maximum of 3 years or the occurrence of one of the following events, whichever occurs first:

- a recommendation of discontinuation by the investigator or Sponsor,
- a decision by the subject to discontinue for any reason,
- an administrative decision is made to end the study

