4. Vital signs: blood pressure and heart rate will be measured prior to injection on dosing days. When available, an automated BP device is recommended for collection of BP and the result recorded to the nearest mmHg. The subject should be sitting at rest for at least 5 minutes prior to these assessments. One assessment for each vital sign (HR, BP) is required per applicable visit.
5. See [Section 7.1.6.3](#) for details of specific tests to be analyzed
6. See [Section 7.1.6.1](#) and [Section 7.1.6.2](#) for details of specific tests to be analyzed
7. Urinalysis collection is prior to the injection; supplies from the central laboratory must be used to perform the urinalysis
8. Only in women of childbearing potential (performed locally, prior to any dosing, using central laboratory kit supplies and with results prior to injection; urine pregnancy test). Results of the pregnancy test from Day 540 of the feeder study will be used on Day 1 in ORION-8
10. Subjects who received blinded placebo in the feeder study will receive blinded inclisiran and subjects who received blinded inclisiran in the feeder study will receive blinded placebo on Day 1 in ORION-8. Subjects moving over from the ORION-3 trial will not receive any treatment at Day 1; all subjects were on inclisiran in the feeder trial and will receive their first dose of inclisiran in this study at day 90
11. Subjects will be observed in the clinic for 30 minutes post injection in order to have additional vital and/or laboratory assessments completed if needed. For any suspected episode of anaphylaxis, the investigator will need to collect a blood sample for tryptase within 30 minutes of an onset of anaphylaxis (or as soon as logically possible).
12. Concomitant medications (relevant) and AE/SAE collection for this study will begin at time of consent and continue through EOS. Ongoing concomitant medications and AEs/SAEs from the feeder study will continue to be followed in this study until resolution.

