### **2.7.1 Adverse events (AEs)**

The most recent version of MedDRA before DBL will be used for coding AEs. An AE will be counted as an ORION-8 treatment emergent AE (TEAE) if the AE started on or after ORION-8 baseline or the AE was present prior to ORION-8 baseline but increased in severity on or after

ORION-8 baseline. Since the investigators are required to enter any worsened AE as a separate record, implementation-wise an AE is a TEAE as long as its onset date/time  $\geq$  date/time of ORION-8 baseline.

The following summaries will be presented for ORION-8 TEAEs using number and percentage of subjects with the event:

- Overall Summary of TEAEs
- TEAEs by primary SOC and PT
- TEAEs by PT
- TEAEs by primary SOC, PT, and maximum severity
- TEAEs possibly related to study drug by primary SOC and PT
- Treatment Emergent Serious AEs (TESAEs) by primary SOC and PT
- TESAEs by PT
- TESAEs possibly related to study drug by primary SOC and PT
- TEAEs leading to withdrawal of study treatment by primary SOC and PT
- TEAEs with a fatal outcome by primary SOC and PT

Subject data listings will be presented for AEs with a fatal outcome, SAEs, and AEs leading to drug discontinuation. Those listings will include all AEs in ORION-8 database, regardless of whether they are ORION-8 TEAE.

If more than one event occurred with the same SOC/PT for the same subject, the subject will be counted only once for that SOC/PT, using the most severe occurrence for the summary by severity.

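### An AE carried over from a feeder study that proves fatal or stops study drug in ORION-8 without a recorded severity increase enters no SOC/PT incidence table

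*SAP*

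**What the plan says.** SAP 2.7.1 defines a TEAE in two branches. The first is new onset: "An AE will be counted as an ORION-8 treatment emergent AE (TEAE) if the AE started on or after ORION-8 baseline". The second is an event where "the AE was present prior to ORION-8 baseline but increased in severity on or after" that baseline. Both are programmed as one date test. "Since the investigators are required to enter any worsened AE as a separate record", the SAP reasons, "implementation-wise an AE is a TEAE as long as its onset date/time" is on or after ORION-8 baseline. Protocol 10.3.4.1 has the same two branches.

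The SAP 2.7.1 incidence tables are all of ORION-8 TEAEs, including the fatal-outcome table and "TEAEs leading to withdrawal of study treatment by primary SOC and PT". SAP 2.7.2 on deaths says "TEAEs with a fatal outcome will be summarized by SOC and PT" and otherwise adds only a listing. The listings of fatal AEs, SAEs and AEs leading to drug discontinuation are not filtered by TEAE status.

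The protocol brings feeder events into this study. The notes to Table 6-1 (Protocol 6.1) state: "Ongoing concomitant medications and AEs/SAEs from the feeder study will continue to be followed in this study until resolution".

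**The concern.** A TEAE filter normally removes events that began before the drug was started. Here that is true only of the Placebo-Inclisiran group. Inclisiran-Inclisiran subjects were treated with inclisiran in ORION-9/10/11, and the Table 6-1 notes say that all ORION-3 subjects were on inclisiran. For these two groups ORION-8 baseline falls in the middle of treatment, so the same filter means different things in adjacent columns of one table.

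Long-term safety and tolerability is a primary objective (Protocol 2.1, SAP Table 1-1). An AE that began on inclisiran in the feeder study and later ends treatment or life is directly relevant to it. If the AE's severity is not recorded as having risen, its onset date keeps it out of the tables by cause. The reader of the study report would then see a fatal-AE table and a withdrawal table that may not cover every such event in ORION-8.

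**Working it through.** The plan gives no figure to reproduce. The check is to trace what happens to a fatal or treatment-stopping AE under the written rules.

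| Case | TEAE? | SOC/PT table? | Source |
|---|---|---|---|
| A. Onset on or after ORION-8 baseline | Yes | Yes | SAP 2.7.1 |
| B. Earlier onset, severity rises, new record entered | Yes | Yes | SAP 2.7.1 |
| C. Onset date unknown or partial and cannot be placed before baseline | Yes, by default | Yes | SAP 5.1.2 |
| D. Earlier onset, no recorded rise in severity | No | No | SAP 2.7.1, 2.7.2 |

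Only case D is affected.

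1. **Can case D occur?** Yes. Protocol 8.2.1 grades severity on three points, with severe at the top and no fatal grade. An AE already severe at baseline cannot rise further when it becomes fatal. An AE of any grade can also lead to stopping treatment by persisting unchanged. The SAP does not say that becoming fatal, or leading to withdrawal, counts as worsening.

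2. **Where does case D appear?** It appears in the SAP 2.7.1 listings. SAP 2.3.1 also summarises early discontinuation with reasons, overall and by feeder group, and Protocol 4.4 includes AE and death among the reasons. SAP 2.4.1 tabulates reasons for missed injections. None of these summaries gives SOC or PT.

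3. **Does it reach MACE?** Yes. SAP Appendix 5.2 builds CV death from fatal events, but the SAP 2.7.1.1.2 summaries are of ORION-8 TEAEs. A case D cardiac death is therefore not counted there.

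4. **Scale.** Change in overall incidence = k / N × 100, where k is the number of omitted subjects.
 - N = 2991 (enrolment given in the Amendment 2 rationale): 1 / 2991 × 100 = 0.033 percentage points per subject.
 - N = 3300 (planned maximum): 1 / 3300 × 100 = 0.030 points.
 - k is not in the documents. If k is assumed to be 1 to 10, the understatement with N = 2991 is 0.03 to 0.33 points.

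 The 2991 figure comes from the amendment that added ORION-3 as a feeder, so the final denominator may differ. Within a single feeder group the denominator is smaller and each subject weighs more.

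**The case against.** The case for leaving the plan alone is substantial.

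- **The SAP follows the protocol's TEAE definition and leans towards inclusion.** Worsened events are tabulated and undated events default to TEAE. This stands, and it confines the gap to case D.
- **The events are not lost.** A reader might infer that these deaths and withdrawals go uncounted. They do not: the listings show each one with its term, and disposition counts AE and death reasons with no TEAE filter. Protocol 4.4.1 asks subjects who permanently stop study drug to return for an EOS visit, so disposition should capture most treatment withdrawals too. What is missing is the breakdown by cause and its rate by group.
- **The class should be rare.** Protocol 4.3 excludes uncontrolled or serious disease that may interfere with participation or put the subject at significant risk, severe noncardiovascular disease that may shorten life expectancy below three years, and active liver disease. This stands.
- **The analysis is descriptive and noncomparative.** No test or decision rule depends on these counts. This stands and limits the consequence.

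Three stronger readings are also tempting. One is that the filter removes events mostly from the Inclisiran-Inclisiran group. The rule is identical for all groups and the documents give no carried-over AE counts, so only its differing meaning by group is supported. Another is that the AE tables are bound to contradict disposition. Disposition counts leaving the study and the AE table counts withdrawal of treatment, so the two need not match under any onset rule. The third is that the Swedish amendment adds a large further loss, since it was written "to collect any safety information during the gap between feeder's EOS and Day 1 of this study" and that gap precedes baseline. However, ORION-9/10/11 subjects join the Safety Population only once dosed in ORION-8, and the size of the gap group is not given.

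**Conclusion.** The point holds in a narrow form. A carried-over AE that proves fatal or stops study drug in ORION-8 without a recorded severity increase is in no SOC/PT incidence table. It remains visible in the listings and, if the subject left the study, as a reason without a cause in disposition. For two of the three feeder groups such an AE may have begun on inclisiran, so the usual ground for a TEAE filter does not apply to them.

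The effect on overall incidence is probably small, at about 0.03 percentage points per omitted subject. Any total rests on an assumed number of cases. The conclusion also assumes that investigators update the outcome of the existing record when an AE becomes fatal or stops treatment at unchanged severity. If they opened a new record with a new onset date, the event would be tabulated. How the feeder studies reported these AEs cannot be checked, because their plans are not part of these documents.

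The change is worth making because it completes the primary safety counts by cause at little cost. It is not evidence that the safety results would be materially wrong.

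**What to change.** 1. **SAP 2.7.2:** add a summary of all deaths on or after ORION-8 Day 1 in the Safety Population, by SOC/PT and feeder group, whatever the TEAE status of the causal AE. Show the TEAE subset within it.
2. **SAP 2.7.1:** add a count of all AEs leading to withdrawal of study drug in ORION-8, split by onset before or after ORION-8 baseline. Keep the planned TEAE table.
3. **SAP 2.7.1.1.2 and Appendix 5.2:** apply the same rule as in item 1 to the CV-death component of MACE.

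The cost is some SAP wording and a changed filter in two or three tables. The listings already pull these records, and SAP 2.1.1 already uses the date of death.

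The downside is that counts may rise slightly. In Placebo-Inclisiran subjects the added events began before any inclisiran, so the new summaries must be shown by feeder group and not only overall.
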